Compare safety and tolerability of the RP2D in two infusion schedules of SQP33 (3-day vs 5-day) in locally advanced, unresectable, STS who are anthracycline naïve and with defined anthracycline sensitive (expected historical ORR ~20%) histologies angiosarcomas, leiomyosarcoma, liposarcoma, synovial sarcoma, adult fibrosarcoma, and undifferentiated pleomorphic sarcoma.

Each treatment group will maintain the total dose of SQP33 per cycle constant and compare 2 different infusion schedules, a 3-day vs a 5-day schedule. The study will be guided by the Continuous Reassessment Method (CRM) design. The CRM model provides an indication of whether to alter the RP2D regimen (3-day dosing per 21-day cycle vs. 5-day dosing per 21-day cycle) based on a comparison of toxicity and efficacy data collected from participants enrolled. The participants will receive SQP33 at the RP2D administered IV as a 3-day dosing regimen per 21-day cycle or as a 5-day dosing regimen per 21-day cycle.

A toxicity rate at or above 15% for myelosuppression (Grade ≥ 3) related treatment emergent adverse events (TEAEs) (anemia and febrile neutropenia) would be considered unsafe for the cohort, and enrollment would stop. If the 3-day infusion is not well tolerated that group will close, the study will continue with the RP2D and 5-day schedule with the initial adaptive design phase.

Safety Monitoring

All available safety tolerability data will be presented and discussed at the SRC. The maximum inefficacy and minimum efficacy rates are based on historical ORR, with <20% ORR being undesirable, and >35% ORR being desirable. Up to 11 participants per arm will be enrolled. After approximately half (n=6 per arm) of participants in Expansion Group 2 have been enrolled and observed for at least 2 cycles or approximately 6-weeks and have had at least one post-baseline tumor assessment, an evaluation of all available data (safety, efficacy, and PK from both the Expansion and Dose Escalation parts of the study) will be performed by the SRC.

Group 3a: Head and Neck

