Group 2 and the use of the CRM model provides an indication of whether to alter the RP2D regimen (3-day dosing per 21-day cycle vs. 5-day dosing per 21-day cycle) based on a comparison of toxicity and efficacy data collected from enrolled participants. The indicated population for the Group 2 participants is locally advanced or metastatic, unresectable, soft-tissue sarcoma of intermediate or high grade with evidence of disease progression and no prior anthracycline treatment, and thus the test statistics parameters for the CRM are based on historical toxicity and efficacy rates of said population (Table 10). The participants will receive SQP33 at the RP2D administered IV as a 3-day dosing regimen per 21-day cycle or as a 5-day dosing regimen per 21-day cycle. Participants may be replaced if they are enrolled into the study but do not receive (for reasons other than AEs/SAEs) the intended dose during Cycle 1. If Cycle 1 cannot be completed due to a COVID-19 infection, an additional patient may be enrolled in the cohort.

Table 10: Continuous Reassessment Method Design Considerations

Parameters	Continuous Reassessment Method (CRM)
Historical Rates of Toxicity ²	
 • Anemia: Grade ≥ 3- [8%] • Febrile neutropenia Grade ≥ 3- [~20%]
Acceptable threshold for toxicity	Grade ≥ 3 Related Myelosuppression TEAEs* 
 • Anemia: Grade ≥ 3- <15% • Febrile neutropenia Grade ≥ 3- <15%
Maximum Inefficacy proportion ²⁻⁴	0.20
Minimum Efficacy proportion ²⁻⁴	0.35
Types I and II errors set at	0.05
Total number of pts per arm	11
Power	none

*Myelosuppression TEAEs as per NCI-CTCAE v5.0- Anemia: Grade 3: Hgb <8.0 g/dL; <4.9 mmol/L; <80 g/L; transfusion indicated. Grade 4: Life-threatening consequences; urgent intervention indicated; Febrile Neutropenia: Grade 3-ANC <1000/mm³ with a single temperature of >38.3 degrees C (101 degrees F) or a sustained temperature of >=38 degrees C (100.4 degrees F) for more than one hour. Grade 4: Life-threatening consequences; urgent intervention indicated.

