Test statistics parameters are based on historical toxicity and efficacy rates (Table 10). The acceptable threshold for toxicity is set at 15%, respectively. A toxicity rate at or above 15% for myelosuppression (Grade ≥ 3) related treatment emergent adverse events (TEAEs) (anemia and febrile neutropenia) would be considered unsafe for that cohort, and enrollment would stop. The maximum inefficacy and minimum efficacy rates are based on historical objective response rates (ORR), with <20% ORR being undesirable, and >35% ORR being desirable.

After approximately half (n=6 per arm) of participants in Group 2 have been enrolled and observed for at least 2 cycles or approximately 6-weeks and have had at least one post-baseline tumor assessment, an evaluation of all available data (safety, efficacy, and PK from both the Expansion and Dose Escalation) will be performed by the SRC, to determine whether to continue to enroll up to a total of 11 participants per arm or to stop enrollment of a cohort.

Groups 1 and 3a will treat up to approximately 28 participants in Stage 1 and Group 2 will treat up to a total of 22 participants. For all Expansion Groups: Patients may be replaced if they are enrolled into the study but do not receive (for reasons other than AEs/SAEs) the intended dose

during Cycle 1. If Cycle 1 cannot be completed due to a COVID-19 infection, an additional patient may be enrolled in the group.

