3. PHASE 2A EXPANSION OBJECTIVES AND ENDPOINTS

3.1 Primary Objectives

Further investigate the safety and tolerability profile of SQ3370 in anthracycline naïve patients with:

- Group 1: Neo-adjuvant treatment of patients with STS of the extremity who are ineligible for primary surgical resection and under consideration for possible/probable amputation, with predefined anthracycline sensitive tumors.
- Group 2: Patients with unresectable, locally advanced or metastatic STS, with predefined anthracycline sensitive tumors and compare safety and tolerability of the RP2D in two infusion schedules of SQP33 (3-day vs 5-day).
- Group 3a Patients with relapsed or metastatic squamous-cell head and neck cancer

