Group 1 - Extremity STS: A sample size of 46 is required to test a null hypothesis of $H_0: \pi \leq 0.2$ (20%) versus an alternative hypothesis of $H_1: \pi \geq 0.35$ (35%) (Seddon 2017; Tapp 2017; Chawla 2015) with a one-sided significance level of 0.0498 and 70.5% power, where π is

the true proportion of successes. This design results in an expected sample size of 25.91 and a probability of early termination of 0.648. If the number of responses is less than or equal to 3 out of 15 participants in the first stage, then the trial will be stopped. If the trial proceeds to the second stage, 46 patients in total will be studied. If 13 or less responses are observed, then the drug is rejected.

Group 3a - Head & Neck: A sample size of 26 is required to test a null hypothesis of $H_0: \pi \leq 0.2$ (20%) versus an alternative hypothesis of $H_1: \pi \geq 0.45$ (45%) (Sandler 1984; Harrington 2001) with a one-sided significance level of 0.049 and 85.1% power, where π is the true proportion of successes. This design results in an expected sample size of 16.28 and a probability of early termination of 0.747. If the number of responses is less than or equal to 3 out of 13 participants in the first stage, then the trial will be stopped. If the trial proceeds to the second stage, 26 patients in total will be studied. If 8 or less responses are observed, then the drug is rejected.

Continuous Reassessment Method (CRM) design Group 2 (Unresectable STS)

Sample sizes for Group 2 participants are guided by the Continuous Reassessment Method (CRM) design (Wheeler 2019). The use of evaluating additional participants in the Expansion

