Group 2 and the use of the CRM model provides an indication of whether to alter the RP2D regimen (3-day dosing per 21-day cycle vs. 5-day dosing per 21-day cycle) based on a comparison of toxicity and efficacy data collected from enrolled participants. The indicated population for the Group 2 participants is locally advanced or metastatic, unresectable, soft-tissue sarcoma of intermediate or high grade with evidence of disease progression and no prior anthracycline treatment, and thus the test statistics parameters for the CRM are based on historical toxicity and efficacy rates of said population (Table 10). The participants will receive SQP33 at the RP2D administered IV as a 3-day dosing regimen per 21-day cycle or as a 5-day dosing regimen per 21-day cycle. Participants may be replaced if they are enrolled into the study but do not receive (for reasons other than AEs/SAEs) the intended dose during Cycle 1. If Cycle 1 cannot be completed due to a COVID-19 infection, an additional patient may be enrolled in the group.

Continuous Reassessment Method Design Considerations

| Parameters | Continuous Reassessment Method (CRM) |
|--|---|
| Historical Rates of Toxicity ² | 
 • Anemia: Grade ≥ 3 [8%] • Febrile neutropenia Grade ≥ 3 [~20%] |
| Acceptable threshold for toxicity | Grade ≥ 3 Related Myelosuppression TEAEs* 
 • Anemia: Grade ≥ 3 <15% • Febrile neutropenia Grade ≥ 3 <15% |
| Maximum Inefficacy proportion ²⁻⁴ | 0.20 |
| Minimum Efficacy proportion ²⁻⁴ | 0.35 |
| Types I and II errors set at | 0.05 |
| Total number of pts per arm | 11 |
| Power | none |

*Myelosuppression TEAEs as per NCI-CTCAE v5.0- Anemia: Grade 3: Hgb <8.0 g/dL; <4.9 mmol/L; <80 g/L; transfusion indicated. Grade 4: Life-threatening consequences; urgent intervention indicated; Febrile Neutropenia: Grade 3-ANC <1000/mm³ with a single temperature of >38.3 degrees C (101 degrees F) or a sustained temperature of ≥ 38 degrees C (100.4 degrees F) for more than one hour. Grade 4: Life-threatening consequences; urgent intervention indicated.

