8.5 Treatment Comparisons

The following labels for dose level will be used on all tabulations, in the following order:

| Phase 2A Expansion | | | | |
|--|---|---|---|-----------------|
| Group 1 Extremity STS 5-Day Infusion (N=00) | Group 2 Unresectable STS 3-Day Infusion (N=00) | Group 2 Unresectable STS 5-Day Infusion (N=00) | Group 3A Head and Neck 5-Day Infusion (N=00) | Total (N=00) |

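### Group 2's size and its 3-day versus 5-day decision are credited to a CRM that is named but not specified, and the SAP defines no between-schedule estimate for a comparison it lists as an objective

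*Protocol*

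**What the plan says.** Protocol 8.3, repeated in substance in the synopsis and 3.5.1, bases Group 2 on a continual reassessment method and gives that method a decision role: "the use of the CRM model provides an indication of whether to alter the RP2D regimen". Phase 2a SAP section 4 agrees: "Sample sizes for Group 2 participants are guided by the Continuous Reassessment Method (CRM) design".

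Table 10 and its SAP counterpart are the whole specification. They list historical toxicity rates, a toxicity limit, response bounds of 0.20 and 0.35, 11 patients per arm, a row reading "Types I and II errors set at | 0.05", and a power row reading none. The Protocol 8.3 text adds "The acceptable threshold for toxicity is set at 15%, respectively" and, for response, "with <20% ORR being undesirable, and >35% ORR being desirable".

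Enrolment is a maximum: "Up to 11 participants per arm will be enrolled" (Protocol 3.5.1), with a Safety Review Committee look at about 6 per arm. SAP 7.1 adds a response rule for that look: with 12 patients over both schedules, 2 or fewer responders stops and 3 or more may continue to 22. SAP section 5 states that there is no randomization.

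The Group 2 primary objective in SAP 3.1 (Protocol 2.2.1.1) includes the aim to "compare safety and tolerability of the RP2D in two infusion schedules of SQP33 (3-day vs 5-day". The same comparison is a listed Group 2 endpoint in Protocol 2.2.2.2 and SAP 3.5. The SAP section headed Treatment Comparisons (8.5) opens "The following labels for dose level will be used on all tabulations, in the following order" and contains only column labels.

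**The concern.** A CRM updates a dose-toxicity model over ordered dose levels and uses it to choose the next level. Group 2 has two schedules with the same total dose per cycle, so there is no dose ladder. The text gives no toxicity ordering between the schedules and no model to update. The method cannot supply the indication the protocol assigns to it, and it does not explain 11 per arm.

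The SAP does not replace it. The one numerical response rule, in 7.1, pools the schedules and so cannot inform a choice between them. No difference, ratio, interval or decision criterion between schedules is defined for toxicity or response.

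At stake is what Group 2 can claim. A reader would take the schedule decision to be model-based. In practice the committee and later the study report would have two adjacent columns of small counts, with nothing showing how far they could differ by chance.

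**Working it through.** **1. Does the method reproduce the plan's other designs?** Exact enumeration of the two Simon designs gives:
- Group 1 (3/15, 13/46; 0.20 vs 0.35): alpha 0.0498, power 0.705, expected size 25.91. All match.
- Group 3a (3/13, 8/26; 0.20 vs 0.45): alpha 0.0498 (stated as 0.049), power 0.851, expected size 16.28. These match apart from truncation of alpha.

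**2. Does 11 per arm follow from Table 10?** A CRM cannot be run, because no skeleton, prior, model, cohort size or update rule is given. The stated inputs (0.20, 0.35, errors of 0.05) can be tried in standard designs.

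Two-sample, pooled variance, mean rate 0.275, one-sided:

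n = [1.645 × √(2 × 0.275 × 0.725) + 1.645 × √(0.20 × 0.80 + 0.35 × 0.65)]² / 0.15²

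= (1.0387 + 1.0239)² / 0.0225 = 189.1, so 190 per arm. Two-sided, it is 228.

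Single-arm exact: 98 patients (27 or more responders). With 11 patients, a cut of 5 or more gives alpha 0.0504 and power 0.33.

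None of these gives 11. The table also conflicts with itself, since a type II error of 0.05 means 95% power while the power row says none.

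**3. Does SAP 7.1 supply the missing basis?** It cites 70% power and one-sided 0.10 with 2/12 as the first-stage limit and 22 in total, but states no final cut. Exact results for 0.20 vs 0.35:

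| Final cut | Alpha | Power |
|---|---|---|
| 7 or more of 22 | 0.122 | 0.667 |
| 8 or more of 22 | 0.054 | 0.515 |

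Neither meets both stated figures. The timing table in the same section marks the Simon evaluation as not applicable to Group 2. The change table in SAP 16 records no change from the protocol.

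**4. How precise would a between-schedule estimate be?** Assume both arms reach 11. With Wilson limits (l, u) for each arm, the Newcombe 95% interval for d = p1 − p2 is:

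d − √[(p1 − l1)² + (u2 − p2)²] to d + √[(u1 − p1)² + (p2 − l2)²]

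Wilson limits: 1/11, 0.016 to 0.377; 2/11, 0.051 to 0.477; 3/11, 0.097 to 0.566.

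- 2/11 vs 2/11: d = 0; half-width √(0.130² + 0.295²) = 0.323, so ±32 points.
- 3/11 vs 1/11: d = 0.182; lower 0.182 − √(0.175² + 0.286²) = −0.154; upper 0.182 + √(0.293² + 0.075²) = 0.484. That is −15 to +48 points.

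**5. How does the 15% stop interact with this?** One event in 6 is 16.7% and two in 11 is 18.2%, both at or above 15%. Suppose the limit is applied literally to one composite event at 6 per arm, with assumed true rates of 30% and 15%. Both arms pass only if neither has an event: 0.70⁶ × 0.85⁶ = 0.118 × 0.377 = 0.044. The precision in step 4 is therefore conditional on both arms being allowed to reach 11.

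**The case against.** The strongest reply is that Group 2 does have working rules and does report by schedule. There is a toxicity limit of 15% that stops a cohort, the 3-day arm closes if it is not well tolerated, and the committee reviews safety, efficacy and PK at 6 per arm. Tables carry a column per schedule, response and disease control rates have exact 95% intervals by expansion group, and PK is left to a separate plan. Table 10 openly states no power, and descriptive reporting is defensible for at most 22 patients. The Phase 2a SAP text is also marked version 0.1. All of this stands.

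It rules out several stronger readings that a reader might infer. The documents do not support saying that Group 2 has no analysis: what is missing is a comparative estimate. Nor can one say that no toxicity target is stated, or that 11 per arm is fixed. A reader might also calculate that, at true rates of 30% and 15%, the worse schedule would tie (14.3%) or look better (13.0%) in 27% of trials. That figure assumes both arms always reach 11 and ignores the 15% stop, so it does not describe this trial.

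A further fair point is that an interval covers chance only. Allocation is not randomized, so a between-schedule difference also carries selection bias, and at 11 per arm even 3/11 versus 0/11 would not exclude zero. This governs how the estimate is labelled. It does not justify leaving the estimate out or keeping the CRM attribution.

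**Conclusion.** The point holds in this form. Group 2's size and schedule indication are attributed to a design that neither document specifies and that does not fit two schedules of equal total dose. Table 10 does not yield 11 per arm: the nearest conventional readings need 98 (single arm) or 190 to 228 per arm. The CRM text, the 15% stop and SAP 7.1's pooled Simon rule are not reconciled. A comparison placed within a primary objective and listed as a Group 2 endpoint has no defined between-schedule estimate.

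The intervals of ±32 and −15 to +48 points assume that both arms reach 11 and that the counts are as shown. They carry no allowance for non-random assignment. The sample-size figures assume that the stated response bounds and errors are the intended inputs. None of this requires Group 2 to be powered or tested formally. It should be corrected before the Phase 2a SAP is finalized.

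**What to change.** - **Protocol synopsis, 3.5.1 and 8.3; SAP 2.3 and 4:** remove the CRM as the basis for size and for the schedule decision. Describe Group 2 as a non-randomized, descriptive comparison of two schedules with up to 11 patients per arm and a review at 6 per arm. Remove the error-rate and power rows, or make them consistent.
- **SAP 7.1:** reconcile the CRM text, the 15% stop and the pooled Simon rule, so that Group 2 has one stated set of rules. Say which of them bear on the choice of schedule. Which clinical stopping limit applies is for the sponsor to settle. Record the change in SAP 16.
- **SAP 8.5, 11 and 12:** add the 3-day minus 5-day difference with a Newcombe 95% interval for Grade 3 or higher related anemia or febrile neutropenia, any Grade 3 or higher related TEAE, SQP33 reduction or stop for an adverse event, and ORR. Label these descriptive and open to selection bias, and state the precision given above for arms that reach 11.

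The cost is wording in both documents and one summary table. No patients are added. The stated design will look less sophisticated, but it will match what Group 2 can deliver.

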1.4. BENEFIT-RISK ASSESSMENT

The study will be performed in accordance with ethical principles that have their origin in the Declaration of Helsinki and are consistent with International Council for Harmonisation (ICH), Good Clinical Practice (GCP), and applicable regulatory guidelines.

Because this is the first study to evaluate SQ3370 in humans, its clinical benefits and safety are not fully known; however, both the SQL70 biopolymer and SQP33 protodrug are based on approved products with well-established safety profiles, and conventional Dox has demonstrated anticancer activity across a range of tumor types. Thirty-nine patients were enrolled and treated in the Phase 1, and thirty-eight patients are evaluable for safety as one patient's treatment was halted day 2 due to COVID-19. Thirty-two of the thirty-nine patients are sarcomas. Thirty patients were treated on the dose expansion protocol with escalating doses of SQP33 from 0.38x to 15x Dox equivalent dose. Eight patients were treated in the 20 mL SQL70 biopolymer cohort, five at the 4x Dox equivalent and three patients at the 6x doxorubicin equivalent dose of SQP33. One patient was treated at the low dose/fragile cohort at 8x Dox equivalent dose of SQP33. Note that patients remain on study treatment at the time of this update. In the Phase 1 the MAD was 15x while the study defined DLT was not established. The sponsor in consultation with the investigators decided not to continue dose escalations. The treatment was well tolerated as published in the ESMO Congress 2022 Poster 1499P, with the most frequent treatment emergent adverse events (TEAEs) being nausea, fatigue, diarrhea or constipation, and decreased appetite. Hematologic toxicities were neutropenia, anemia, and thrombocytopenia. As of 9/27/2022, an analysis of Grade 3 or greater TEAEs was performed through Cohort 8 (12x Dox equivalent). In the 20 mL SQL70 biopolymer group, TEAEs >10% of the total and in >1 patient showed worsening anemia in 3 patients (37.5%) and neutropenia in 2 patients (25%). In the 10 mL SQL70 biopolymer dose expansion, grade 3 or greater TEAEs >10% of the total and in >1 patient showed **worsening anemia** in 4 patients (16.7%). The totality of available data supports the continuation of the study and opening of the Phase 2a. Nonetheless, SQ3370 is a new treatment and there may be both unexpected risks and benefits not previously associated with conventional Dox or NaHA treatments. See the Investigator's Brochure for additional details.

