3.2.7. Safety Review Committee (Dose Escalation and Phase 2a)

The SRC will include the study team led by the medial monitor, and the active Investigator(s). The SRC will review all available safety data at the completion of Cycle 1 for each cohort to evaluate possible DLTs, recommend whether more patients should be enrolled at a given dose level / cohort, and whether to dose escalate or to stop enrollment based on the definition of DLTs in addition to its members' best clinical judgement and will provide recommendations to the sponsor.

With agreement from the sponsor, the dose escalation scheme may be modified (e.g., smaller increases or decreases in dose may be permitted, infusion timing, duration, or schedule may be modified) based on available PK and pharmacodynamic data, and/or the timing and severity of AEs observed. Changes that can only be made with a protocol amendment will include:

- Dose level escalations that are increased by larger increments than the scheme in the protocol
- Administration of more than 5 SQP33 infusions per cycle
- Administration of more than 20 mL of SQL70 biopolymer per cycle

Phase 2a Responsibility

In Phase 2a, the SRC will utilize the same criteria to evaluate the safety and tolerability of all available safety data at the completion of timing for each group to determine the initial safety and monitor the groups throughout the study overall safety and tolerability.

Table 4: Phase 2a Safety Evaluation Timing

Group	Run-in Evaluation N= (timing)	Simon 2 Stage 1 evaluation	Final Assessment
1: Extremity STS	N=6 (after cycle 1)	N=15	N=46
2: STS unresectable	N=12 (6 per arm; after cycle 2)	N.A.	N=22
3a: Head and Neck	N.A.	N=13	N=26

N.A.= Not Applicable

A run-in is not planned for the Head & Neck group (Group 3a) since they will be receiving the RP2D and schedule of SQ3370 without modifications (see [Table 4](#)).

Group 1 will receive SLQ70 in a volume of 20 mL with the RP2D of SQP33 and therefore the safety lead-in to this group is warranted. The SRC may, after the planned initial review of any group, within its purview recommend additional monitoring to the sponsor.

[figure not shown]

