6.14.3. Phase 2a Expansion Groups

Blood (plasma) samples for determination of PK levels of SQP33 protodrug, SQL70 biopolymer and active Dox following SQ3370 treatment as well as to explore the kinetics of SQP33 protodrug degradation under pH, temperature, and other conditions to be collected from patients in each of the Expansion Groups at the time points below:

Expansion Group 1: Extremity STS [Stage 1 Only]***Stage 1 Only*****Cycle 1:**

- Day 1 pre-infusion of SQP33 protodrug; at 15 minutes post-infusion; and at 2 and 4 hours post-infusion.
- Day 2, 3, and 4 pre-infusion of SQP33 protodrug and at 15 minutes post-infusion.
- Day 5 pre-infusion of SQP33 protodrug; at 15 minutes post-infusion; and at 2 and 4 hours post-infusion.

Cycle 2:

- Days 1, 3, and 5 pre-infusion of SQP33 protodrug and at 15 minutes post-infusion.

Note: Post dose PK timings are based on the end time of the SQP33 protodrug infusion, not the start.

Expansion Group 2: Unresectable STS***3-Day Infusion cohort*****Cycle 1:**

- Day 1 pre-infusion of SQP33 protodrug; at 15 minutes post-infusion; and at 2 and 4 hours post-infusion.
- Day 2 pre-infusion of SQP33 protodrug and at 15 minutes post-infusion.
- Day 3 pre-infusion of SQP33 protodrug; at 15 minutes post-infusion; and at 2 and 4 hours post-infusion.

Cycle 2:

- Day 1 pre-infusion of SQP33 protodrug and at 15 minutes post-infusion.
- Day 3 pre-infusion of SQP33 protodrug and at 15 minutes post-infusion.

5-Day Infusion cohort**Cycle 1:**

- Day 1 pre-infusion of SQP33 protodrug; at 15 minutes post-infusion; and at 2 and 4 hours post-infusion.
- Day 2, 3, and 4 pre-infusion of SQP33 protodrug and at 15 minutes post-infusion.
- Day 5 pre-infusion of SQP33 protodrug; at 15 minutes post-infusion; and at 2 and 4 hours post-infusion.

Cycle 2:

- Days 1, 3, and 5 pre-infusion of SQP33 protodrug and at 15 minutes post-infusion.

Note: Post dose PK timings are based on the end time of the SQP33 protodrug infusion, not the start.

Expansion Group 3a: Head and Neck

Cycle 1:

- Days 1 and 5 pre-infusion of SQP33 protodrug; at 15 minutes post-infusion; and 2 and 4 hours post-infusion.

Note: Post dose PK timings are based on the end time of the SQP33 protodrug infusion, not the start.

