6.19. ADMINISTRATION OF INVESTIGATIONAL PRODUCT

Figure 5 and Figure 6 below illustrates one cycle of IP administration. See section 5.3 [Investigational Product Dosage and Administration](#) and the study-specific Pharmacy Manual for additional details. Group 2: Unresectable STS will have a cohort that receives their dose of SQP33 protodrug in 3 days, instead of 5 days.

Figure 5: SQ3370 5-Day Administration Schedule

[figure not shown]
[figure not shown]

Figure 6: SQ3370 3-Day Administration Schedule

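### Group 2's 15% toxicity stop is worded for different units in the protocol and the SAP and has no patient count, and Table 10's 0.05 error rates cannot be met at Group 2's sample sizes.

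*Protocol*

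**What the plan says.** **Protocol.** Section 8.3 says a Group 2 toxicity rate at or above 15% "would be considered unsafe for that cohort, and enrollment would stop". Section 3.5.1 has the same sentence: "would be considered unsafe for the cohort, and enrollment would stop". For Group 2, the protocol uses cohort for a schedule arm: section 6.14.3 labels the "3-Day Infusion cohort", and section 6.19 says Group 2 "will have a cohort that receives their dose of SQP33 protodrug in 3 days, instead of 5 days". Table 9, however, heads the whole head-and-neck and extremity groups as cohorts.

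**Phase 2a SAP.** Section 2.3 repeats the stop sentence but names the expansion group; section 4 says only group. Section 2.3 then says the 3-day arm closes if poorly tolerated while the 5-day schedule continues. Section 7.1 frames the Group 2 review as going on to 22 patients or stopping. Section 1 says the SAP supersedes the protocol's statistical considerations, and the change table in section 16 reads N/A.

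**Events, timing and errors.** Protocol 8.3 adds: "The acceptable threshold for toxicity is set at 15%, respectively". Table 10 gives anemia and febrile neutropenia each a limit below 15%, while the stop sentence names them together. The stop is not tied to the 6-per-arm review, and under protocol 3.2.7 the Safety Review Committee (SRC) is also to "monitor the groups throughout the study overall safety and tolerability". The Table 10 row "Types I and II errors set at" reads 0.05, the row for power reads none, and neither says which endpoint it covers.

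**The concern.** A stopping rule should give one answer from one set of data. This one gives a cut-off and names a continual reassessment design. It does not say which patients form the denominator, whether the rate is observed or model-based, or how many patients trigger it. At the same review SAP 7.1 does print a count for response: 2 or fewer of 12 stops, 3 or more may continue.

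Comparing the safety of the two schedules is Group 2's purpose, so whether the stop falls on one arm or on both matters. It is also the only numeric toxicity stop written specifically for Group 2. The 0.05 entry adds to the problem: a reader would take it as an assurance about error rates that 11 patients per arm cannot provide.

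**Working it through.** No toxicity boundary is printed, so there is no plan figure to reproduce. As a check on the method, the exact binomial calculation returns the printed Group 1 Simon design (alpha 0.0498, power 70.5%, early termination 0.648, expected size 25.91).

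**Inputs.** Threshold 15% (protocol 8.3). Review at 6 per arm, 12 in total (protocol Table 4). Maximum 11 per arm, 22 in total (Table 10, Table 4). Historical anemia 8% and febrile neutropenia about 20%; response 20% versus 35% (Table 10). Using 8% as acceptable and 20% as unacceptable toxicity is my assumption; the documents name no such pair.

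**Step 1: smallest count with a raw rate of at least 15%.**
- 6 patients: 1 (1/6 = 16.7%)
- 11 patients: 2 (2/11 = 18.2%; 1/11 = 9.1%)
- 12 patients: 2 (2/12 = 16.7%; 1/12 = 8.3%)
- 22 patients: 4 (4/22 = 18.2%; 3/22 = 13.6%)

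**Step 2: stop probabilities at one look with 6 per arm, true rate p.** A given arm: 1 − (1 − p)^6. At least one arm: 1 − (1 − p)^12. Both arms: the square of the first. Pooled: P(X ≥ 2) with X ~ Bin(12, p). Exactly one event in 12: 12p(1 − p)^11. In that last case one arm meets the cut-off and the pooled group does not.

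| True rate | Given arm | At least one arm | Both arms | Pooled | Exactly one of 12 |
|---|---|---|---|---|---|
| 8% | 39.4% | 63.2% | 15.5% | 24.9% | 38.4% |
| 15% | 62.3% | 85.8% | 38.8% | 55.7% | 30.1% |
| 20% | 73.8% | 93.1% | 54.4% | 72.5% | 20.6% |

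The look schedule matters too. If the pooled raw rate were checked after every patient up to 12, the stop probability would be 44.1% at 8% and 82.8% at 20%.

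**Step 3: the choice of statistic.** As a raw rate, 1 of 6 is enough. If an exact one-sided 95% lower bound had to exceed 15%, 3 of 6 would be needed (bound 15.3%; at 2 of 6 it is 6.3%).

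**Step 4: the 0.05 entry.** The raw per-arm rule stops at a true 8% with probability 39.4% and fails to stop at 20% with probability 1 − 0.738 = 26.2%. The table below takes, for each size, the smallest cut-off with type I error at or below 0.05, and shows the resulting type II error.

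| n | Toxicity 8% vs 20%: cut-off, type I, type II | Response 20% vs 35%: cut-off, type I, type II |
|---|---|---|
| 6 | 3, 0.009, 0.90 | 4, 0.017, 0.88 |
| 11 | 4, 0.009, 0.84 | 6, 0.012, 0.85 |
| 12 | 4, 0.012, 0.79 | 6, 0.019, 0.79 |
| 22 | 5, 0.027, 0.54 | 9, 0.020, 0.65 |

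A higher cut-off only raises type II error, and a lower one takes type I above 0.05. No cut-off at these sizes meets both. For 20% versus 35%, an exact single-arm test with both errors at 0.05 needs about 98 patients. A type II error of 0.05 would also mean 95% power, where Table 10 says none, and SAP 7.1 builds its Group 2 response rule on 70% power and one-sided 0.10.

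**The case against.** The strongest reply is that the unit difference is terminology. SAP 8.1 lists each Group 2 arm among the Phase 2a expansion groups, and 8.5 gives each its own column, so expansion group can itself mean one arm. SAP 2.3 calls the 3-day arm a group. The Phase 2a SAP replaces cohort with group widely, including in the Simon table and the patient-replacement sentence, which fits an empty change table. Protocol Table 9 shows that cohort is not used strictly either. Most of this stands, and it is why per arm is the better-supported reading. It does not remove the conflict: SAP 2.3 also uses Expansion Group 2 for both arms together, and 7.1 offers only going on to 22 or stopping.

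It is also fair to object that comparing one given arm with the pooled group is not like for like. The working therefore adds the either-arm and both-arm figures. On the given-arm measure the two readings differ by only 1.3 points at 20% (73.8% against 72.5%).

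A reader might infer that two events in the 3-day arm would shut a 5-day arm with none, or that pooling would force a toxic arm to continue. The documents support neither. The sentence after the stop rule keeps the 5-day schedule open when the 3-day infusion is poorly tolerated, and the SRC reviews all data and may act at any time under protocol 3.4.

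**Conclusion.** The point holds as an inconsistency in a stopping rule and as an unattainable error-rate entry. It should not be read as two deliberately different rules: the SAP declares no change, and its own table layout treats each arm as an expansion group. Read literally, though, the texts give different answers whenever exactly one of the first 12 patients has an event, which has probability 38.4% at a true 8% and 20.6% at 20%. Those figures illustrate a raw proportion, one look at 6 per arm, one event type, independent patients, the same rate in both arms, and rates that apply over the follow-up available at the look. The documents fix none of these.

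The 0.05 result does not depend on which unit is chosen. With type I error at or below 0.05, type II error is at least 54% for 8% versus 20% toxicity and about 65% or more for 20% versus 35% response. Table 10 does not say that 0.05 applies to toxicity, so it cannot be called a broken toxicity guarantee; it is unmet for either endpoint at the rates used here.

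The sponsor should correct this. SRC oversight limits the practical harm, and loose terminology keeps confidence in the unit conflict at medium.

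**What to change.** 1. Reconcile protocol 3.5.1 and 8.3 with SAP 2.3, 4 and 7.1 on whether the stop applies to an arm or to all of Group 2, and on whether 15% applies to anemia and febrile neutropenia separately or combined.
2. Print the sponsor's own rule as patient counts at the 6-per-arm review and at any later look, name the statistic behind it, and say whether it also applies between reviews. Give its stop probabilities at true rates of, for example, 5, 8, 15, 20 and 30%.
3. Delete the 0.05 entry, or replace it with the error rates the design has and the endpoint they refer to, in Table 10, its synopsis copy and SAP section 4.

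The cost is a paragraph and a small table in each document. The Phase 2a SAP carries a version 0.1 footer with an incomplete date, so it appears still to be a draft. Writing the existing rule as counts does not change its strictness. Choosing a looser count would: 2 of 6 would stop an arm 7.7% of the time at a true 8% but only 34.5% at 20%. The threshold and its strictness stay with the sponsor.
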